A peripheral nerve monitor may be used to monitor the degree of residual neuromuscular blockade. This is standard anaesthetic equipment with the most common mode to assess residual blockade used being a train of four count. This involves adhesive dots applied over the ulna nerve and a current applied (approximately 70-80mA) in a train of four impulses 0.5 seconds apart with a pulse width of 250 microseconds. It is a safe method of assessing the occupancy of

acetylcholine receptors at the neuromuscular junction by observing the number of twitches displayed in the peripheral muscle (e.g thumb movement).

Number of twitches

- 0- 100% receptors blocked
- 1- 90% receptors blocked
- 2- 75-80% receptors blocked
- 3- 75% receptors blocked
- 4- 0% receptors blocked

For the purposes of our study we plan to continuously monitor the train of four count and ratio using a peripheral nerve stimulator module that is built into the anesthesia machine (GE Datex Ohmeda). The train of four count on both measuring tools will be delivered as a train of four impulses 0.5 seconds apart (2Hz) at 70-80mA with a pulse width of 250 microseconds.

Our current approach does not involve routine measurement of the degree of residual neuromuscular blockade with a peripheral nerve stimulator. This is a safe approach as monitoring is achievable with partial blockade but may not necessarily be most beneficial in patients with existing neurological impairment as complete reversal of neuromuscular blockade is not ensured.(Li, Song et al. 2010)

The issues with this current technique are;

- a) Patients cannot be monitored for neurological changes during their transfer into the prone position
- b) There is likely residual neuromuscular blockade decreasing the amplitude of motor evoked potentials

A cases series of 10 patients in healthy subjects undergoing lumbar spine surgery demonstrated a 74% increase in mean amplitude of the MEPs with reversal of neuromuscular blockade with sugammadex 2mg/kg.(Batistaki, Papadopoulos et al. 2012)

We plan to perform a randomised controlled cross over trial comparing the change in MEP amplitudes with administration of sugammadex or placebo. This will be performed on at risk patients (e.g. cervical myelopathy) undergoing posterior cervical spine surgery where MEPs can be more difficult to attain but of higher utility.(Kombos, Kopetsch et al. 2003)

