The crossover arm of the trial is to enable patients to function as their own control group. During surgical closure patient will remain on a total intravenous anaesthesia (propofol and remifentanil). When the patient returns to a train of four count of 2 or more on peripheral nerve monitor repeat motor evoked potentials will then be recorded and

patients will receive the alternate drug to the one received in the initial arm of the trial.

The purpose of this study is to determine the increase in amplitude of the motor evoked potentials when residual neuromuscular blockade is reversed with sugammadex or placebo.

4. Hypothesis

We hypothesize that reversal of neuromuscular blockade by sugammadex will increase the amplitude of motor evoked potentials compared with placebo.

5. Significance of the study

Facilitating increased amplitudes of MEPS via reversal of residual neuromuscular blockade will enable increased accuracy of monitoring.

Providing the option of reversal of neuromuscular blockade will allow MEPs to be monitored during patient positioning to prevent placing them in a neurologically compromising position.

6. Methods

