6.1 Research Design

This is a prospective, single centre, triple blinded randomised controlled cross-over trial. Patients who are scheduled for an elective posterior cervical spine procedure in prone position and require motor evoked potential monitoring (MEPs) will be included. Patients will be randomised to assign to one of the following treatment sequences: sugammadex followed by placebo, or vice versa. The primary outcome is the change of MEP amplitude of the first dorsal interossei from baseline 3 minutes after administration of the allocated intervention. The patients, anesthesiologists and neurophysiologists (outcome assessor) will be blinded for the allocated intervention group.

The first study intervention will be performed after the patients are positioned in prone with a train of four count of 2 and satisfactory baseline motor evoked potentials have been recorded. This will likely occur during or just prior to surgical exposure.

The second study intervention will be performed during surgical closure. This will be once the surgeons have completed their use of motor evoked potentials and the patient remains on total intravenous anaesthesia (propofol and remifentanil). A minimum washout period of 100 min after the last bolus dose of rocuronium (equivalent to 5 half lives) is required and the completeness of washout will be confirmed with no residual tetanus fade, fade on train of four (or fading in double burst stimulation) on a peripheral nerve stimulator. The operative time

of posterior cervical spine procedure is usually around 3 hours and should allow complete washout of rocuronium. After the preconditions are achieved on peripheral nerve stimulator or the direct train of four monitor, the second intervention (either sugammadex or placebo) will be administered.

On each occasion the increase in amplitude of the motor evoked potential of both upper and lower limbs will be assessed at 3,6,9,12 and 15 minutes post intervention.

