7.2 Study Protocol

Patients should undergo peripheral nerve monitoring following the induction via a peripheral nerve stimulator and by a direct train of four monitor by the neurophysiologists. The train of four should be assessed on peripheral nerve stimulator and on the neurophysiology monitoring prior to turning the patient prone. If the patient has two or more twitches on either monitoring they should be given 0.1mg/kg rocuronium prior to positioning prone.

Once the patient is in their final position for surgery the anaesthetic will be changed to a total intravenous anaesthetic (TIVA) with propofol and remifentanil titrated to entropy of 40-60. The volatile anaesthesia has to be washed out with high flows of 10L/min until end tidal desflurane is less than or equal to 0.2.

When the above conditions are met the train of four count (TOFC) will be checked by the anaesthesiologist. When the TOFC is 2 or more the baseline motor evoked potentials (bMEPs) will be performed.

Following the bMEPs the anaesthesiologist will administer the reversal drug (either sugammadex 2mg/kg in 10 ml syringe or matching placebo). This time must be strictly recorded, as it is the time that has elapsed since the induction dose of muscle relaxant. The neurophysiologist will perform and record MEPS at 3,6 and 9 minutes post reversal dose. The following parameters will continuously be monitored during the study period: TOFC, Entropy, BP, HR, CO2,

peak airway pressures, anaesthetic infusion rates, temperature and oxygen saturation. If the testing occurs during surgical exposure it is important to ask the surgeons to make a very brief pause to allow the motor testing to be performed and to check the entropy at the same time.

Following surgery commencement there will be a surgical grading of the relaxation of the surgical field once exposure attained and collection of surgeon stated observation of patient movement.

The operative time of posterior cervical spine procedure is usually around 3 hours and should allow for complete washout of rocuronium. A minimum washout period of 100 min after the last bolus dose of rocuronium (equivalent to 5 half-lives) is required and the completeness of washout will be confirmed with no residual tetanus fade, no fade on train of four (or fading in double burst stimulation) on a peripheral nerve stimulator.

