The crossover arm of the trial will occur during surgical closure at the end of the operation when the surgeons have finalised their use of the monitoring and the patients are still receiving total intravenous anaesthesia (propofol and remifentanil). If needed, each patient will be given 0.1mg /kg rocuronium to facilitate surgical closure. When the train of four count is of 2 or more the patients will be administered the cross-over drug (placebo if received sugammadex initially and vice versa) and the motor evoked potentials and same anaesthetic variables as above will be recorded for 3,6 and 9 minutes post cross-over dose.

8. Assessment

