8.2 Outcome Measurements

Primary Outcome Measure

The primary outcome measure is the increase in amplitude of the motor evoked potential measurements of the first dorsal interosseous muscle at 3 minutes following reversal of residual muscle relaxation with either sugammadex or placebo.

Secondary Outcome Measures

- Changes in the amplitude of the MEPs from the baseline in the first dorsal interosseous muscle at 6 and 9 minutes

- Side effects of reversal (hemodynamic changes, respiratory changes, surgeon observed patient movement, requirement for additional muscle relaxation and the anesthetic agents)
- Grading of relaxation of the surgical field by the surgeons using a four-point Likert scale (poor, acceptable, good and optimal) .

9. Data Collection and Management

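### The period-2 dosing rule does not ensure residual block, so placebo-first patients can be given sugammadex with nothing to reverse

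*Combined protocol and SAP*

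**What the plan says.** The rules for the second period are spread over several places.

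- **Washout.** Sections 6.1 and 7.2 require at least 100 minutes since the last rocuronium bolus. In section 7.2, "the completeness of washout will be confirmed with no residual tetanus fade, no fade on train of four".
- **Re-dose.** Section 7.2, crossover paragraph: "If needed, each patient will be given 0.1mg /kg rocuronium to facilitate surgical closure".
- **Trigger.** The same paragraph continues: "When the train of four count is of 2 or more the patients will be administered the cross-over drug". No upper limit on the count or the TOF ratio is given.
- **Design summary.** Section 6.1 moves from the washout conditions to dosing without mentioning a re-dose: "After the preconditions are achieved on peripheral nerve stimulator or the direct train of four monitor, the second intervention" is then given.
- **Crossover rationale, end of the Background.** "When the patient returns to a train of four count of 2 or more on peripheral nerve monitor repeat motor evoked potentials" are recorded and the alternate drug is given. This wording presupposes block but does not require it.

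For the first period, section 7.2 ties the same rocuronium dose to the twitch count: "If the patient has two or more twitches on either monitoring they should be given 0.1mg/kg rocuronium prior to positioning prone".

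The TOF table in the Background reads "4- 0% receptors blocked" for four twitches. The primary outcome (section 8.2) is the rise in first dorsal interosseous amplitude "at 3 minutes following reversal of residual muscle relaxation with either sugammadex or placebo".

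**The concern.** The washout rule puts every patient in a state of no detectable block. The only step that could restore block is optional, and its stated purpose is surgical closure, not the experiment. A fully recovered patient has four twitches, which satisfies a trigger of 2 or more. Nothing in the text stops the second drug being given in that state.

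This matters most for the placebo-first sequence, whose only sugammadex dose falls in period 2. If sugammadex raises the amplitude less without block than with it, each placebo-first patient who is not re-dosed pulls the pooled effect toward zero. How many do so depends on how often surgeons want relaxation at closure, which has nothing to do with the trial question. Continuous TOF monitoring would reveal the problem only after dosing, and the plan does not say what to do then. The risk is a missed or understated effect, not a false positive.

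**Working it through.** **1. Reproduce the plan's sample size.** Inputs from section 10.2: difference 1200 microV, within-patient SD 1600 microV, two-sided 0.05, 80% power, 30 patients raised to 40.

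- Normal approximation for a 2x2 crossover: N = 2 × 1600² × (1.960 + 0.842)² / 1200² = 27.9, so 28.
- Noncentral t with N − 2 degrees of freedom: the SD of the within-patient difference is √2 × 1600 = 2263, and the standard error is 2263/√N. N = 29 gives power 0.786 and N = 30 gives 0.801. The stated 30 is reproduced.
- Drop-out: 30/(1 − 0.25) = 40, as stated.

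The plan names no crossover test. The t-test is used below because it returns the plan's own N.

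**2. Dilution.** Two quantities are assumed, since the documents give neither:

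- *f*: the share of placebo-first patients given sugammadex without block;
- *g*: their response as a share of 1200 microV.

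Block is taken to be present in period 1. The effect is then 1200 in the sugammadex-first sequence and 1200 × [1 − f(1 − g)] in the placebo-first sequence. With 1:1 allocation the crossover estimate averages the two:

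pooled effect = 1200 × [1 − f(1 − g)/2].

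Example, f = 0.5 and g = 0: 1200 × 0.75 = 900 microV. With N = 30 the standard error is 2263/√30 = 413, the noncentrality is 900/413 = 2.18, and power is 0.557.

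**3. Results for g = 0** (no response without block)

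| f | Pooled effect (microV) | t-test power, 30 completers | t-test power, 40 completers | Mann-Whitney power, 30 completers | Completers for 80% (t-test) |
|---|---|---|---|---|---|
| 0 | 1200 | 80% | 90% | 79% | 30 |
| 0.25 | 1050 | 69% | 82% | 68% | 40 |
| 0.50 | 900 | 56% | 69% | 53% | 52 |
| 0.75 | 750 | 42% | 53% | 39% | 74 |
| 1 | 600 | 29% | 37% | 26% | 114 |

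The Mann-Whitney column is simulated, because section 11 names that test: 10,000 runs, normal changes with SD 1600, no added between-patient variance, changes pooled over periods.

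**4. Sensitivity**

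- With g = 0.5, t-test power at 30 completers is 75%, 69%, 62% and 56% for f = 0.25, 0.5, 0.75 and 1.
- If all 40 complete and g = 0, power stays at 80% only up to f of about 0.29.
- The t-test figures ignore the extra variance from mixing blocked and unblocked patients. Including it lowers 0.557 to 0.543 at f = 0.5, N = 30.

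**The case against.** **Re-block was intended.** The crossover paragraph runs from rocuronium, to waiting for the count, to the drug. It addresses each patient, and the Background speaks of the count returning. Waiting for a count of 2 makes sense only if it had been lower. The preconditions in section 6.1 may also mean the TOF condition and not just the washout check, because they name both monitors. This is a fair reading of intent. It does not bind the anaesthesiologist: the condition qualifies the whole sentence, its stated purpose is closure, and no section makes block mandatory.

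**Period 1 has the same open trigger.** Section 7.2 says 2 or more there too, while section 6.1 says 2. This stands. But period 1 follows an intubating dose and a count-triggered top-up, whereas period 2 follows required full recovery, so the gap lies mainly in period 2. A common window closes both.

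**The size is conditional.** This also stands. The steepest losses need most or all placebo-first patients to go without a re-dose and not to respond. At f = 0.10 and g = 0, power is 76% with 30 completers and 81% with 34 (15% drop-out from 40). If the true rise is the 74% cited in section 10.2, that is 0.74 × 2000 = 1480 microV. Power at 30 completers with g = 0 is then 93%, 86% and 74% for f = 0, 0.25 and 0.5. A larger true effect cushions the power but not the understatement: the estimate is still reduced by the proportion f(1 − g)/2.

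**The remedy is not free or certain.** It gives a relaxant without surgical need near the end of the case. Nothing in the documents shows that 0.1 mg/kg brings a recovered patient to a count of 2 to 3, particularly one given sugammadex earlier. This is why the fix needs a rule for a re-dose that fails.

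**Conclusion.** The concern holds. Followed exactly as written, the plan allows sugammadex to be given in period 2 to a patient with no block, which contradicts the outcome in section 8.2. That the rule leaves this open is certain from the text. How much harm follows is not, because it rests on f and g, which the documents do not supply.

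If every patient is in fact re-blocked, the design works as planned. If half the placebo-first patients are not, and they do not respond, a quarter of the effect is lost and power falls from 80% to 56% with 30 completers. The bias is toward no effect. This should be corrected before the trial runs, because no analysis can recover a reversal effect from patients who had nothing to reverse.

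**What to change.** Put one dosing rule into the crossover rationale in the Background, section 6.1, and both the period-1 and crossover paragraphs of section 7.2:

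1. The no-fade check is the washout step only.
2. After it, re-establish block in every patient with the 0.1 mg/kg rocuronium already in section 7.2, and delete the words *if needed*.
3. Record a new baseline amplitude before the second drug. The Background says this; the crossover paragraph of section 7.2 omits it.
4. Give the study drug in both periods within the same residual-block window, with an upper limit: for example a TOF count of 2 to 3, the exact window to be set by the clinicians.
5. State what is done if the re-dose does not bring the count into the window, identically for both sequences. Keep such patients in the analysis by randomised sequence, because the period-2 count is measured after randomisation.

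Record the TOF count, TOF ratio and any re-dose at each baseline. Keep the pooled effect as primary and report effects by period only as a descriptive sensitivity analysis. In a 2x2 crossover, treatment-by-period is aliased with carryover, and a period-specific comparison on the plan's inputs has only about 51% power (15 v 15) or 64% (20 v 20).

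**Cost.** The changes are to wording in four places. TOF is already monitored, and the planned sample size stays the same provided the re-dose usually works. Clinically, some patients receive rocuronium they would not otherwise have had, closure may involve a short wait, and residual block is possible at the end of the case in those given placebo second. Section 7.1 already recommends TOF assessment at that point, with neostigmine and glycopyrrolate reversal where appropriate.

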8.1 Baseline Measurements

At the time of enrollment, the following data will be collected for all participants: patient demographics, preoperative neurological function, comorbidities, allergies, baseline physiological variables (blood pressure, heart rate, O₂ saturations, weight) and procedure details.

8.2 Outcome Measurements

Primary Outcome Measure

The primary outcome measure is the increase in amplitude of the motor evoked potential measurements of the first dorsal interosseous muscle at 3 minutes following reversal of residual muscle relaxation with either sugammadex or placebo.

Secondary Outcome Measures

- Changes in the amplitude of the MEPs from the baseline in the first dorsal interosseous muscle at 6 and 9 minutes

- Side effects of reversal (hemodynamic changes, respiratory changes, surgeon observed patient movement, requirement for additional muscle relaxation and the anesthetic agents)
- Grading of relaxation of the surgical field by the surgeons using a four-point Likert scale (poor, acceptable, good and optimal) .

9. Data Collection and Management

9.1 Data Collection

The following data will be collected (see attached Data Collection Form):

Administrative Data

Screening log- detailing numbers of potential participants screened for inclusion and reasons for exclusion and numbers actually recruited.

Demographic data

Age, sex, height, weight, American Society of Anaesthesiologists physical class (ASA)

Study Data

Baseline data as detailed in section 8
Outcome data as defined in section 8

9.2 Data Management

An electronic data management system will be used. All data will be entered directly on the electronic system. Data will be acquired on a Research laptop and also the Monitoring Laptop of the neurophysiologist. Following the case, data will be transferred from the Neurophysiologist laptop to the Research database where it will later be analysed.

Pre specified automated data entry checks will be performed on all entered data to prevent the entry of impossible values or the omission of key data fields. All study databases will be in the password protected UHN server. Any data containing participant identifying details will be stored separately and securely from study documents.

10. Sample Size

10.1 Hypotheses

Null Hypothesis- There is no difference between the amplitude of the baseline motor evoked potentials before and after reversal with sugammadex or placebo.

Alternative Hypothesis- There is a difference in the amplitude of the baseline motor evoked potentials before and after reversal with sugammadex or placebo.

10.2 Sample size

A previous observational study reported sugammadex increased the amplitude of MEP by 74% (Batistaki, Papadopoulos et al. 2012). The normal upper limb MEP amplitude (first dorsal interosseus) is 2000 +/- 1600 microV from a previous published cross-over study in MEP (Chong, Manninen et al. 2014). Based on the assumption that the within-patient standard deviation of the MEP amplitude is 1600 microV and a power of 80%, a total of 30 patients is required in this two-intervention crossover study for detecting a treatment difference of 1200 microV (60% increment) at a two-sided 0.05 significance level. The sample size will be increased to 40 patients (20 patients per group) to cater for a potential 15-25% drop-out rate during the study.

11. Analysis

Statistical analysis will be performed using SPSS statistical software (version 14). The data distributions will be tested for normality with the Kolmogorov-Smirnov test. Descriptive statistics will be summarised as mean (\pm SD), median [Interquartile range (IQR)] or number (%) as indicated. The Mann-Whitney U test will be performed to compare the amplitude values of the two groups. TOF count, grades of surgical relaxation will be compared using the Chi-square test or Fisher's exact test according to the expected counts. In all cases, a P-value of 0.05 will be considered statistically significant.

12. Ethical aspects

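### The 80% power in section 10.2 is derived for one MEP amplitude per period, while the primary outcome is a change from baseline for which no SD is given

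*Combined protocol and SAP*

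**What the plan says.** **Outcome.** Section 6.1: "The primary outcome is the change of MEP amplitude of the first dorsal interossei from baseline 3 minutes after administration of the allocated intervention". Section 8.2 agrees in substance: "The primary outcome measure is the increase in amplitude of the motor evoked potential measurements of the first dorsal interosseous muscle at 3 minutes". The null hypothesis in section 10.1 is also a before-and-after statement: "There is no difference between the amplitude of the baseline motor evoked potentials before and after reversal with sugammadex or placebo".

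**Sample size.** Section 10.2 gives the source of its variability figure as "The normal upper limb MEP amplitude (first dorsal interosseus) is 2000 +/- 1600 microV from a previous published cross-over study in MEP". It then proceeds: "Based on the assumption that the within-patient standard deviation of the MEP amplitude is 1600 microV and a power of 80" per cent. The target difference is 1200 microV, two-sided 5%, giving 30 patients, raised to 40 for a drop-out of 15-25%.

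**Analysis.** Section 11 works on amplitudes, not changes: "The Mann-Whitney U test will be performed to compare the amplitude values of the two groups".

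**Baseline.** Section 7.2 fixes the first one: "When the TOFC is 2 or more the baseline motor evoked potentials (bMEPs) will be performed", before the first study drug. For the second period the text is less clear. The paragraph on the crossover arm at the end of the background, just before section 4, has MEPs recorded again before the alternate drug is given. Section 6.1 points the same way: "On each occasion the increase in amplitude of the motor evoked potential of both upper and lower limbs will be assessed". The crossover paragraph of section 7.2, which is the operational text, lists only the recordings at 3, 6 and 9 minutes after the second dose. No section says which baseline the second-period change is taken from.

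**The concern.** The quantity that was sized (an amplitude) is not the quantity named as primary (a change in amplitude). A change score carries the noise of two readings, so a crossover contrast of two changes can involve four readings instead of two. Whether that raises or lowers the variance depends on how closely the errors of the baseline and 3-minute readings move together, which the plan does not state, and on whether there are one or two baselines, which it leaves open.

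At stake is how a null result would be read. If the trial finds no significant difference, nobody could say from the plan what power it had for its own primary outcome. The choice between amplitude and change score, and between one baseline and two, would also still be open when the data are in hand.

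**Working it through.** **Inputs from section 10.2:** within-patient SD of the amplitude 1600 microV; difference 1200 microV; two-sided 5%; 30 completers. With 40 enrolled, completers are 40 x 0.75 = 30 to 40 x 0.85 = 34.

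**Assumed, because the plan does not give it:** r, the correlation between the within-patient errors of the baseline and 3-minute readings in the same period, after the patient's own level is removed. It is shown from 0 to 0.75. Further assumptions are equal SDs at both readings, independent errors across periods, and a paired crossover analysis (noncentral t, n - 2 degrees of freedom).

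**1. The plan's own figure.** With one amplitude per period, the contrast is S - P.
- SD = sqrt(2) x 1600 = 2263.
- Noncentrality at 30 = 1200 / (2263 / sqrt(30)) = 2.905.
- Power is 78.6% at 29 and 80.1% at 30, so 30 reproduces exactly.
- Other readings do not give 30: taking 1600 as the SD of the difference gives 16-17 patients, and parallel groups give 56 in total.

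**2. Change score, one common baseline B.** (S - B) - (P - B) = S - P. The baseline cancels, power is again 80.1%, and 30 stands.

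**3. Change score, a baseline in each period.** Each change has variance 2 x 1600² x (1 - r), and the contrast of two changes has SD = 1600 x sqrt(4(1 - r)).

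| r (assumed) | contrast SD | power, n = 30 | n = 34 | n = 40 |
|---|---|---|---|---|
| 0 | 3200 | 51% | 56% | 64% |
| 0.25 | 2771 | 63% | 69% | 76% |
| 0.5 | 2263 | 80% | 85% | 90% |
| 0.75 | 1600 | 98% | 99% | 99.6% |

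The r needed for 80% power is 0.50 at 30, 0.43 at 34 and 0.32 at 40.

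r is not the ordinary correlation between readings across patients. That correlation is (sb² + r x 1600²) / (sb² + 1600²), with sb the between-patient SD. For r = 0.5 it is 0.60 if sb = 800 and 0.75 if sb = 1600 (both values of sb assumed).

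**4. If 1600 is a total SD.** The within-patient SD is then smaller. If half the variance lies between patients (assumed), it is 1600 x sqrt(0.5) = 1131. The contrast SD at r = 0 is 2 x 1131 = 2263, and raw-change power at 30 is 80%, 90% and 98% for r = 0, 0.25 and 0.5. With 30% of the variance between patients (assumed), it is 66%, 78% and 92%.

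**5. Three-minute amplitude adjusted for the difference between period baselines.** This model has treatment and period effects and a baseline in each period, with 1600 within-patient. Simulated with 20,000 trials per setting, power at r = 0, 0.25, 0.5 and 0.75 is:
- n = 30: 79%, 81%, 88-89%, 98-99%
- n = 34: 83%, 86%, 92-93%, 99%
- n = 40: 90%, 91%, 96%, over 99%

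Type I error at n = 30 was 0.051 (r = 0) and 0.050 (r = 0.5). The closed formula, SD = 1600 x sqrt(2(1 - r²)), gives 89.8% at r = 0.5. That is slightly optimistic because it ignores estimation of the covariate slope.

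**The case against.** The strongest reply is that no sample-size error has been shown. The arithmetic of 10.2 is right for an amplitude contrast, section 11 also compares amplitudes, a common baseline leaves 30 intact, and a raw change score reaches 80% once r is about 0.5. All of that stands.

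The 51% end of the range also needs several things at once: a baseline in each period, an unadjusted change score, a true within-patient SD of 1600, and no shared error between readings taken minutes apart under a controlled anaesthetic. That is an extreme corner. The figure of 1600 is quoted as the spread of an amplitude, so it may be a total SD, in which case power is higher. Against this, section 10.2 expressly assumes that 1600 is within-patient, so the main table takes the plan at its word.

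A reader might infer from the table that the trial is underpowered. The documents do not support that. They give no r and do not settle the baseline, so power for the stated outcome could lie on either side of 80%.

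It can also be said that the unpaired test in section 11 is the larger defect. That is a separate issue. Every figure here assumes a paired analysis, so none is the power of the test as section 11 words it.

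Finally, baseline adjustment is one valid choice among several. The minimum correction is to name one outcome and one baseline, and to give the SD that matches them.

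**Conclusion.** The mismatch is real and should be fixed. Section 10.2 supports 80% power for a difference between two 3-minute amplitudes. Sections 6.1 and 8.2 promise a change from baseline, and nothing in the plan links the two.

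The size is conditional. With one common baseline there is no loss. With a baseline in each period, which the background paragraph and section 6.1 favour but the crossover paragraph of section 7.2 does not confirm, a raw change score has 80% power at 30 only if r is about 0.5 or more. Across assumed r of 0 to 0.75 the power is 51% to 98%. This rests on equal SDs, 1600 being within-patient, and a paired analysis. The conclusion is that power for the primary outcome is not established, not that 30 is too few. Confidence is medium, because r and the nature of the 1600 cannot be settled from the documents.

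**What to change.** 1. Make the primary analysis a within-patient crossover comparison of the 3-minute first dorsal interosseous amplitude, with treatment and period effects, adjusted for the within-patient difference between the two period baselines.
2. Reconcile the crossover paragraph of section 7.2 with the background paragraph on the crossover arm, so that the MEP recording before the second dose is listed.
3. Restate section 10.2 for that analysis. Say whether 1600 is a within-patient or a total SD, and define r as the correlation of within-patient errors. If 1600 is within-patient, give power at 30 as about 79% if r = 0 and about 88-89% if r = 0.5, with r and equal SDs marked as assumptions.
4. Name the same quantity in sections 6.1, 8.2, 10.1, 10.2 and 11.

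If the raw change score is kept instead, state which baseline it uses, the SD of the change, and the power that follows.

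**Cost.** The change needs rewording of those sections and one added line in section 7.2 for a recording the background already describes. It needs no extra patients. The downside is about 1 point of power if r = 0 (78.9% against 80.3% without the covariate, simulated at 30), mainly from estimating the slope. In return, under equal SDs, power stays near the planned 80% at r = 0 and rises as r increases.
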